### **Treatment A**

In this treatment schedule, children will stay in the NRU for 7 days during which period their clinical condition will stabilise, and their mothers or caretakers will have learnt preparation of khichuri and halwa and taking care of the children at home. Thereafter, they will be discharged and health workers will visit them at their homes at regular intervals until they achieve a WH >80%, are free of oedema, and have a good general condition. If a child develops an acute illness or the general condition is not satisfactory at the time of discharge, then the discharge will be postponed till resolution of the illness. During stay in the NRU, calories and protein are gradually increased over a period of time in a programmed way in order to achieve rapid growth involving a weight gain of more than 10 g/kg per day. A major element of the method of nutritional rehabilitation practised in the NRU of the CRSC is that the diet given to the children contains proteins derived mainly from vegetable sources. Food containing animal protein such as milk (which is given only initially), eggs, meat or fish are expensive, and the mothers of these children can hardly afford these foods when continuing nutritional rehabilitation at home.

The diet schedule to be followed for the children is as shown on the following page. This is the standardized diet schedule that is currently being routinely practiced in the NRU of the CRSC.

Diet	Item & amount	Energy intake Kcal/kg.day	Protein intake g/kg.day
1	Milk suji 10 ml/kg.feed (110ml/kg.day) 2 hrly (11 feeds per day)*	74	1.5
	Halwa 10 g/kg.feed 2 feeds per day	48	1.0
	Total:	122	2.5
2	Milk suji 10 ml/kg.feed (110ml/kg.day) 2 hrly (11 feeds per day)*	74	1.5
	Halwa 10 g/kg.feed 2 feeds per day	48	1.0
	Khichuri 10 g/kg.feed 2 feeds per day	29	0.6
	Total:	151	3.1
3	Milk suji 100 10 ml/kg.feed (110ml/kg.day) 2 hrly (11 feeds per day)*	110	2.8
	Halwa 10 g/kg.feed 2 feeds per day	48	1.0
	Khichuri 10 g/kg.feed 2 feeds per day	29	0.6
	Total:	187	4.4
4	Milk suji 100 10 ml/kg.feed (110ml/kg.day) 2 hrly (11 feeds per day) *	110	2.8
	Halwa 10 g/kg.feed 3 feeds per day	72	1.5
	Khichuri 10 g/kg.feed 3 feeds per day	43	0.9
	Total:	225	5.2
5	Milk suji 100 10 ml/kg.feed (40ml/kg.day) 6 hrly (4 feeds per day)	40	1.0
	Halwa 20 g/kg.feed 3 feeds per day	144	3.0
	Khichuri 20 g/kg.feed 3 feeds per day	87	1.8
	Total:	271	5.8

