\* There is a gap in feeding at 4 a.m. Composition of milk suji and milk suji 100 (appendix 2)

Diets 1, 2, 3 and 4 will be provided on days 1, 2, 3 and 4 respectively. These diets ensure 2 hourly feeds with milk suji at least for the first 4-5 days of nutritional rehabilitation. Diet 5 is started when the child achieves an intake of 225 kcal/kg per day, which is possible by day 7. Most of the calorie and protein in diet 5 are derived from halwa and khichuri, the number of milk feeds being only four per day. The child will be given plain water in between the feeds, and breast feeding continued if applicable. The amount of each feed offered and actually taken will be recorded on a feeding chart. Upon discharge, the mother or caretaker will be advised to prepare khichuri and halwa at home and feed the child specified amounts or more for further nutritional rehabilitation. A plastic cup and a spoon will be provided to each child, but ingredients for khichuri and halwa will not be provided. A health worker will calculate the specified amounts of khichuri and halwa using a chart (appendix 3) and instruct the mother regarding the minimum number of cups of the diets to be given to the child each day.

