**Anti-helminthic treatment:** Children >1 year of age will be given mebendazole, 100 mg two times daily for 3 days, if such treatment has not been provided in the last six months. This treatment will be provided after two weeks of nutritional rehabilitation.

**Follow-up:** After the child is discharged from the NRU, a health worker will visit the child every week for one month and then at fortnightly intervals until the child achieves an oedema-free WH >80%. During each visit, the child's general condition will be assessed, weight and height (or length) measured, presence or absence of oedema noted, supplies of micronutrients provided, compliance of feeding and micronutrient supplementation checked by 24 hours recall, and morbidity recorded, if any. To aid recall of morbid conditions, on each visit mothers will be given a pictorial calendar portraying a well child and children with diarrhoea, vomiting, cough, fever, eye infection, or discharging ears [10]. Mothers will be requested to record daily on the calendar whether the condition had been present or absent in the previous 24 hours. Morbidity will then be recorded on a precoded form with the help of the calendar. Diarrhoea will be defined as the passage of three or more watery or liquid stools per day. An episode will be considered new if at least two diarrhoea-free days intervene between the present and previous episodes. The health worker's identification of children with pneumonia of different grades of severity will be based upon WHO guidelines [11]. Lack of weight gain for two consecutive visits will constitute failure to respond. The health worker will refer to the CRSC any child with suspected serious illness, i.e., diarrhoea with some or severe dehydration, pneumonia, ear or throat infection, repeated episodes of fever, loss of appetite, or failure to respond to feeding. Self referral will also be encouraged and entertained at any hour of the day. The child will be evaluated and managed accordingly by any of the investigators (during day time) or the on-duty physician (at night). Readmission to the hospital and the NRU will depend upon existing CRSC guidelines. Any child readmitted to the NRU will not be re-enrolled into the study, but will maintain the pre-readmission status as a study subject. The physician will also record in the precoded form diagnosis, treatment, duration, and outcome of any severe illness including relapse of severe malnutrition or septicemia.

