### **Treatment B**

Children on treatment B will also stay in the NRU for a stabilisation period of 7 days during which their mothers or caretakers will have learnt preparation of khichuri and halwa and taking care of the children at home. Dietary therapy, micronutrient supplementation, training of mothers or caretakers, immunization, and anti-helminthic treatment will be the same as in treatment A. Thereafter, they will be discharged and advised to attend the NFU every week for one month and then at fortnightly intervals until they achieve an oedema-free WH >80%. If a child develops an acute illness or the general condition is not satisfactory at the time of discharge, then the discharge will be postponed till resolution of the illness. The protocol for follow-up will be the same as in treatment A, the difference being that the children will be

brought to the NFU by the parents. If a child fails to attend the NFU within 2 days of a specified follow-up day, a health worker will make a home visit, do the follow-up and reiterate the importance of bringing the child to the NFU for follow-up. The health worker, in course of her follow-up, will try to find out the reason(s) for defaulting. A previous study conducted at the NRU [12] to find out the cause of defaulting showed the principal reason to be the wrong perception of the parents that follow-up was not needed since the child was okay. Other reasons that came up during the previous study, and that will also be inquired during the follow-up visit by the health worker in this study, include: inability of the mother to come to the hospital alone, illness of the mother or child, distance, visit to village homestead, inability to leave other children at home alone, inability to afford the travel expenses, and death of the child.

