### **Outcome Measures**

- Time to recovery (achievement of WH 80%, oedema-free), in days
- Rate of weight gain, in g/kg per day calculated from lowest weight to discharge weight
- Speed of loss of oedema, in days
- Failure to respond
- Morbidity, in number and duration of episodes over equal periods of follow-up for both groups
- Mortality
- Cost of treatment

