## Data Analysis

Describe plans for data analysis. Indicate whether data will be analyzed by the investigators themselves or by other professionals. Specify what statistical softwares packages will be used and if the study is blinded, when the code will be opened. For clinical trials, indicate if interim data analysis will be required to monitor further progress of the study. (TYPE WITHIN THE PROVIDED SPACE).

Data will be analyzed using the SPSS Windows software. The Epi Info software will be used to calculate anthropometric indices. Enrollment characteristics will be compared between the three treatment groups. The outcome variables will be compared both within and between groups from enrollment to discharge. For normally distributed quantitative variables, means will be compared by ANOVA. Variables not normally distributed will be log transformed before analysis. Categorical variables will be compared by Chi-square test, multiple or logistic regression will be performed to minimise bias if required.

Results from all randomized children will be included in the analysis of the study. Data from children withdrawn because of failure to respond, TB, or voluntary dropout will be included in the analysis upto the time of withdrawal. A supplementary analysis excluding the children withdrawn may also be made.

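### In the two home arms, failure to respond is judged on weight alone and the referral list omits oedema, although some children may go home on day 7 still oedematous

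*Protocol*

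**What the plan says.** Enrollment Criteria admit a child with weight-for-height below 70% of the reference median or with oedema. In Treatments A and B the child leaves the nutritional rehabilitation unit (NRU) after 7 days. Postponement is tied to illness or condition: "If a child develops an acute illness or the general condition is not satisfactory at the time of discharge". Loss of oedema is not a condition of discharge.

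After discharge, visits are weekly for one month and then fortnightly. At each visit general condition is assessed, weight and height are measured, and there is an oedema check: "presence or absence of oedema noted". The outcome rule is "Lack of weight gain for two consecutive visits will constitute failure to respond". Suspected serious illness leads to referral. An i.e. introduces the list, which runs from diarrhoea with dehydration through "pneumonia, ear or throat infection, repeated episodes of fever, loss of appetite, or failure to respond to feeding". For Treatment B, "The protocol for follow-up will be the same as in treatment A".

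Elsewhere oedema counts. Recovery is "Time to recovery (achievement of WH 80%, oedema-free), in days", speed of loss of oedema is an outcome of its own, and visits and most micronutrient supplies continue until the child is oedema-free above 80%.

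On eligibility, the committee's memorandum of December 1999 asked that oedematous children be excluded because of the risk of sending them home after 7 days. The investigator's reply asks it to reconsider and accepts that some will be discharged with oedema. The final decision is not in the document.

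**The concern.** Body weight in an oedematous child is tissue plus fluid, so the weight rule can err in two directions.

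- **Missed deterioration.** A child who retains or regains fluid gains weight. The failure rule is not met, and no listed referral reason covers oedema itself.
- **False failure.** A child who is building tissue while losing fluid can show no net gain at two visits and be called a failure.

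Failure to respond is a listed outcome (Specific Aims, Outcome Measures) and a referral reason. It is also a reason for withdrawal: under Data Analysis, "Data from children withdrawn because of failure to respond" are used only up to withdrawal, so a wrong label can also shorten a child's record. The first error is the safety issue, and it touches the risk that the committee raised.

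**Working it through.** The plan gives no figure for this point, so there is none to reproduce. The working sizes the group exposed to the rules.

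**Inputs**
- 75 children per arm, so 150 in A and B (Sample Size).
- One-third of severely malnourished admissions have oedema (reply to the committee). Assumption: the same share holds at enrolment. A 20% share is shown as a lower case.
- Days to loss of oedema in the NRU: median 7, mean 7.0, SD 3.7, n = 41 (same reply). Assumption: days count from NRU entry.
- Median for home-managed children in the earlier Dhaka study: 19 days (same reply).
- Weight gain: 4 g/kg per day assumed for home care with outpatient follow-up, 8.4 in the NRU (Sample Size); 2 is added as a low case.

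**Step 1. Oedematous at entry.** 150 × 1/3 = 50; at 20%, 150 × 0.20 = 30.

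**Step 2. Still oedematous after a given day, at NRU clearance.** The shape of the distribution is not given, so four shapes are used. CV = 3.7/7.0 = 0.53, and the log-normal sigma is √ln(1 + 0.53²) ≈ 0.50.

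| Shape | P(T > 7) | P(T > 14) | P(T > 21) |
|---|---|---|---|
| Normal | 0.50 | 0.029 | 0.0001 |
| Gamma | 0.43 | 0.050 | 0.003 |
| Log-normal, mean 7 | 0.40 | 0.050 | 0.007 |
| Log-normal, median 7 | 0.50 | 0.081 | 0.013 |

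- Discharged with oedema: 50 × (0.40 to 0.50) = 20 to 25 (30 at entry: 12 to 15).
- Past day 14: 50 × (0.029 to 0.081) = 1.5 to 4.1, about 1 to 4 (30 at entry: 0.9 to 2.4).
- Past day 21: 50 × (0.0001 to 0.013) = 0 to 0.7.

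**Step 3. Timing of a false failure.** With discharge on day 7, the first two weekly intervals are days 7–14 and 14–21. For fluid loss to fall in both, oedema must normally last past day 14. At NRU clearance that is the 1 to 4 of 50.

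**Step 4. Fluid loss needed.** Tissue gain per week is the daily gain × 7. At 4 g/kg this is 28 g/kg, or 2.8% of body weight; at 2 it is 1.4%; at 8.4 it is 5.9%. Fluid loss must at least match this in each interval. The documents give no fluid volumes, so the calculation stops here.

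**Step 5. Slower clearance at home.** Assume a log-normal with median 19 days from entry and the same CV. Then P(T > 7) = 0.978, P(T > 14) = 0.731 and P(T > 21) = 0.420. The children at issue are the 20 to 25 who leave with oedema, so the later figures must be conditional on T > 7.
- Past day 14: 0.731/0.978 = 0.75; × 20 to 25 = 15 to 19.
- Past day 21: 0.420/0.978 = 0.43; × 20 to 25 = 9 to 11.

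**The case against.** The strongest reply is that much is already covered. General condition and oedema are looked at on every visit, loss of appetite triggers referral, families may come at any hour, a physician evaluates each referred child, and relapse is recorded. Recovery requires absence of oedema. Rate of weight gain runs from the lowest weight, which limits the effect of fluid loss there. A false failure leads to a medical check, which is the safe direction. Failure to respond is one of seven listed outcomes and does not drive the sample size. The safety question was also argued: the reply cites work finding that oedema alone does not identify children at high risk of dying, and the Dhaka study with 3.5% mortality in both the home and the inpatient groups.

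This limits the harm but does not close the gap. None of these provisions makes persistent, increasing or returning oedema a reason to refer.

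Three stronger readings are tempting and are not supported.
- A reader might take the 20 to 25 as the number misclassified. They are the children exposed; each must also meet the timing and fluid-loss conditions. Slower clearing also spreads the fluid loss over more weeks, which makes it less likely to cancel weight gain.
- A reader might apply the 19-day median to all 50 from entry and get 50 × 0.420 = 21 at day 21. That model leaves 50 × 0.978 = 49 oedematous at day 7, which contradicts the 20 to 25.
- A reader might conclude that oedema lasting to a fixed late day should itself count as failure. The documents give no source for such a cut-off. Adding it in A and B alone would create failures with no counterpart in Treatment C and so bias the comparison. Judging weight only once the child is oedema-free would also delay labelling an oedematous child who gains no weight.

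**Conclusion.** The point holds in limited form. The failure rule and the referral list leave out a sign that the protocol uses for entry, for recovery and at each visit, so the rules as written can miss a child who is gaining fluid and can mislabel one who is losing it. On NRU clearance, about 20 to 25 of an assumed 50 oedematous home-arm children leave with oedema and about 1 to 4 of the 50 remain so past day 14. How many would be misclassified cannot be worked out from the documents and may be small.

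This rests on the one-third share holding at enrolment, on the NRU times applying from entry, and on oedematous children having stayed eligible. Enrollment Criteria as shown admit them. If the committee's exclusion was adopted in the end, the numbers fall to about zero. A reader might infer that the committee's advice was disregarded; the document shows a request to reconsider and no outcome, so that does not follow.

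**What to change.** **Referral (Treatment A, Follow-up, and so Treatment B).** Keep lack of weight gain at two consecutive visits as a referral trigger for every child, oedematous or not. This matters because "ingredients for khichuri and halwa will not be provided", so poor intake at home must still be caught. Add to the list: *oedema that has returned, is increasing, or persists at the second weekly visit after discharge.*

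**Outcome (all three arms).** State one rule: an interval without weight gain does not count towards failure to respond if the child was oedematous at its start and the oedema is clearing; return of oedema is recorded as relapse. In Treatment C, weekly NRU weights take the place of visits while the child is an inpatient.

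**Cost.** A few sentences, with no change to visits, eligibility, arms or sample size. Presence or absence of oedema is already recorded. Judging it as increasing or clearing needs one more entry on the form (less, same or more than last time). The downside is extra evaluations at the second weekly visit, about day 21: 0 to 1 of 50 on NRU clearance, and about 9 to 11 if clearance after discharge follows the cited 19-day home median. Referral is not readmission, which stays under the hospital's existing guidelines.

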### **Hypothesis to be tested:**

1. After an initial period of hospitalization, severely malnourished children recovering from diarrhoea can be managed at home using indigenous, low-cost, and culturally acceptable diets.
2. The cost-benefit of a home-based programme for nutritional rehabilitation of severely malnourished children recovering from diarrhoea will be more than the conventional hospital-based programme.

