### **Specific Aims:**

---

Describe the specific aims of the proposed study. State the specific parameters, biological functions/ rates/ processes that will be assessed by specific methods (TYPE WITHIN LIMITS).

---

1. To plan, organize and establish an effective home-based programme for rehabilitation of severely malnourished children recovering from diarrhoea.
2. To compare by means of a prospective, randomised study, the outcome, including growth, rate of weight gain, speed of loss of oedema, days to achieve oedema-free weight-for-height (WH) 80% of National Centre for Health Statistics (NCHS) median reference, failure to respond to nutritional therapy, morbidity, mortality, and cost of treatment of children managed by home-based nutritional rehabilitation (with follow-up at outpatient clinic or at home) with those managed in the conventional hospital-based programme (definition of failure to respond and morbid conditions are detailed in the *methods* section).

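### The protocol gives two routes for a home-arm child who fails and is readmitted to the NRU, and neither measures whether the child was managed at home

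*Protocol*

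**What the plan says.** The first hypothesis is that, after an initial hospital stay, these children "can be managed at home using indigenous, low-cost, and culturally acceptable diets".

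Four parts of the protocol bear on a home-arm child who does badly:

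- **Treatment A, Follow-up.** Failure is defined: "Lack of weight gain for two consecutive visits will constitute failure to respond". Such a child is referred to the hospital, as are children with suspected serious illness such as pneumonia or dehydrating diarrhoea. Then: "Readmission to the hospital and the NRU will depend upon existing CRSC guidelines". A child readmitted to the NRU is not enrolled a second time but "will maintain the pre-readmission status as a study subject". Treatment B adopts the same follow-up protocol.
- **Outcome Measures.** The recovery outcome is "Time to recovery (achievement of WH 80%, oedema-free), in days". It sets no condition on where recovery takes place or on readmission. Failure to respond is listed separately.
- **Data Analysis.** All randomised children are included, but "Data from children withdrawn because of failure to respond, TB, or voluntary dropout will be included in the analysis upto the time of withdrawal".
- **Treatment C.** Children stay in the NRU until they meet the recovery target.

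**The concern.** Take one clinical course: a child in arm A or B is discharged home, does not gain weight at two consecutive visits, is referred, is readmitted to the NRU and reaches the target there. The protocol can be read to score this child in two ways. Either the child is a continuing subject who has recovered in the home arm, or the child was withdrawn at failure and has no recovery time.

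Hypothesis 1 is about management at home. On the first reading, a child who reached the target in the comparator setting can count towards home recovery. On the second, children for whom home care did not work leave the time-to-recovery comparison, which then rests on those for whom it did. The choice also decides whether weights and costs after the failure enter the analysis. In arm C no child can be readmitted before recovery, so the ambiguity falls on the home arms alone.

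**Working it through.** **The two routes side by side**

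| Step | Child continues (Treatment A, Follow-up) | Child is withdrawn (Data Analysis) |
|---|---|---|
| After failure and readmission | stays a study subject in the allocated arm | data used up to withdrawal only |
| Target reached in the NRU | meets the recovery definition, which ignores setting | not in the analysed data |
| Time to recovery | a value, probably a late one | no value, so nothing to enter a comparison of means by ANOVA |
| Shows recovery at home? | no | no |

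The protocol does not say which column applies to a child readmitted for failure.

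**Direction**

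- Counting the NRU recovery raises the number recovered in the home arm, compared with counting the child as not recovered at home.
- For time to recovery the sign depends on the reference. Compared with dropping the child, keeping a late recovery lengthens the home-arm mean and counts against home care. Compared with treating the child as never recovered at home, it favours home care. The protocol does not settle this.

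**Size**

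The protocol gives no readmission rate and no recovery rate after readmission, so there is no stated figure to reproduce on this point. The denominator can be checked from the Sample Size section: 2 × 7.3² / (8.4 − 4)² × 10.5 = 57.8, rounded up to 58 as stated. Then 58 / 0.8 = 72.5, or 73, close to the stated 75 per group.

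Let r be the share of a home arm readmitted before recovery and s the share of those who then recover in the NRU. Both are assumptions. Children affected = 75 × r × s:

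| r | s = 50% | s = 90% |
|---|---|---|
| 5% | 1.9 children (2.5 points) | 3.4 (4.5 points) |
| 10% | 3.8 (5.0 points) | 6.8 (9.0 points) |
| 20% | 7.5 (10.0 points) | 13.5 (18.0 points) |

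The range is about 2 to 14 children per home arm, or 2.5 to 18 percentage points of the arm, if the first route is followed. On the second route no NRU recovery is counted, and the failures drop out of time to recovery instead.

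**The case against.** A reader might infer that the protocol does score NRU recoveries as home recoveries and so inflates the evidence for home care. The text does not support that:

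- The readmission sentence fixes only study status. It prevents double enrolment and keeps the allocation. It could even be read as freezing the child's outcome status at readmission.
- The withdrawal rule points the other way for children withdrawn for failure.
- Failures are not hidden. The Specific Aims compare "failure to respond to nutritional therapy, morbidity, mortality, and cost of treatment of children managed by home-based nutritional rehabilitation" with hospital care, so a child who fails at home is recorded as a failure whatever follows.
- The listed outcome is time to recovery in days, not the proportion recovered, and a late NRU recovery may count against home care.
- Referral and possible readmission are part of the home programme, and analysing children in their allocated arm is ordinary intention-to-treat practice.
- The Clinical Economics section costs all groups from day 7 after randomisation and does not exclude readmission days.

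Most of this stands, and it limits the point to an unresolved conflict. Two things remain. The separate failure outcome does not cover everything: a child referred for pneumonia or dehydration need not meet the failure definition, and no listed outcome captures readmission as such. Nor can the conflict be put down to detail left for a statistical analysis plan, because the protocol itself states both rules.

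**Conclusion.** The point holds as a conflict between two stated rules, together with a recovery definition that does not match hypothesis 1. A home-arm child who fails and is readmitted can be scored as recovered in the home arm or cut off without a recovery time, and neither result shows management at home. Proven inflation in favour of home care does not follow. The size, and the direction for time to recovery, cannot be derived from the protocol; the 2 to 14 children of 75 rest wholly on the assumed readmission and recovery shares. Keeping readmitted children in their randomised arm is sound and should not change. This is a worthwhile and inexpensive improvement, not a flaw that undermines the randomised comparison.

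**What to change.** 1. Reconcile the follow-up text under Treatment A with the withdrawal text under Data Analysis, so that the handling of data from a child readmitted for failure is stated once. This concerns data only; when to readmit or stop treatment is not at issue here.
2. Keep the comparison of all randomised children on recovery in any setting.
3. For hypothesis 1, add recovery without NRU readmission. Count readmission, withdrawal for failure and death as not recovered, treated as competing events.
4. Show readmission for intercurrent illness separately from readmission for failure to respond, since the first need not mean that home feeding failed.
5. State that readmission days are costed to the allocated arm.

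The cost is one extra analysis. The physician's form already records diagnosis, treatment, duration and outcome of severe illness, including relapse, and hospital records are to be used. The home-arm recovery figure under item 3 will look slightly less favourable than recovery in any setting.
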